7.4.6 Immunogenicity Assessment

Immunogenicity of MEDI-551 will be assessed and summarized descriptively by dose cohort.

7.5 Sample Size and Power Calculations

Arm A

For the dose-escalation phase, a minimum of 18 evaluable subjects (3 subjects each in Dose Cohort 1 through 6) or up to approximately 36 evaluable subjects (3+3 subjects per dose cohort) were required to determine the MTD; 26 were enrolled. A subject was considered evaluable for assessment of DLT if the subject received at least one full cycle (4 doses for Cohorts 1 and 2; 2 doses for Cohorts 3 to 6) of MEDI-551 and completed the safety follow-up through the DLT evaluation period (as defined in Section 4.5.6), or the subject experienced a DLT. Any nonevaluable subject would be replaced in the same dose cohort. Table 7.5-1 provides the probability of dose escalation to the next higher lever for each underlying true DLT rate. For example, for a common toxicity that occurs in 10% of subjects, there is a greater than 90% probability of escalating to the next higher dose level. Conversely, for a toxicity that occurs with a rate of 60%, the probability of escalating to the next higher dose level is less than 10%.

Table 7.5-1 True Underlying DLT Rate at a Given Dose Level

True Underlying DLT Rate	10%	20%	30%	40%	50%	60%	70%	80%	90%
Probability of Escalating Dose	0.91	0.71	0.49	0.31	0.17	0.08	0.03	0.009	0.001

DLT = dose-limiting toxicity.

For the dose-expansion phase, approximately 20 subjects were to be entered into each of 3 arms to determine the preliminary efficacy profile of MEDI-551 in the treatment of advanced CLL (including SLL), DLBCL, and FL. A total of 69 subjects (24 CLL, 21 DLBCL, 23 FL, and 1 MM) were enrolled. The primary objective of the dose-expansion phase was to determine the preliminary efficacy profile of MEDI-551 in these subjects. The sample size estimation was based on the CR rate and the exact binomial test. A total of 20 subjects per arm would be required to have approximately 80% power for testing the following hypotheses at 1-sided significance level of 0.1.

- Null hypothesis: undesirable CR rate = 5%
- Alternative hypothesis: desirable CR rate = 20%

Arms B and C

Dose Escalation

There were 4 planned dose levels (6, 12, 24, and 48 mg/kg) for MEDI-551 in the Arm B dose- escalation phase and 2 planned dose levels (8 and 12 mg/kg) for Arm C dose escalation. Using a standard 3+3 design, approximately 24 to 36 subjects were to be enrolled during the dose-escalation phase in Arms B and C depending on the observed safety profile and total number of dose levels evaluated.

A total of 7 subjects were enrolled in Arm B; all were in dose escalation (n = 3 each for 6 and 12 mg/kg, n = 1 for 24 mg/kg). Based on emerging PK and pharmacodynamic data, a dose of 12 mg/kg, administered weekly during Cycle 1 and then monthly in subsequent cycles, was determined to be sufficient to saturate the B-cell sink and achieve full exposure. At the sponsor's discretion and not due to any safety issues, no further dose-escalation was conducted. The MTD was not reached.

Arm C dose escalation was completed as planned, with 3 subjects each in the 8 and 12 mg/kg cohorts.

Dose Expansion

A sample size of 26 subjects was planned for each dose-expansion cohort in Arms B and C. Given an expected response rate of 50% for both cohorts, this would provide 80% power at a significance level of 0.20 (2-sided) to exclude the historical response rate of 30%, and associated 80% confidence intervals for the response rate would have a precision of $\pm 13\%$. The 30% historical response rate was selected for both Arms B and C expansion cohorts based on the following reported data:

- In relapsed CLL patients, OR rates between 15% and 30% were reported for rituximab monotherapy ([O'Brien et al, 2001](#); [Mavromatis and Cheson, 2003](#)).
- In DLBCL patients with 2 prior lines of therapy, response rates were only about 30% with single-agent rituximab ([Coiffier et al, 1998](#); [Wang et al, 2013](#); [Churpek et al, 2013](#)).

Enrollment in Arm B was discontinued prior to dose expansion at the sponsor's discretion and not due to any safety issues..

Further enrollment in Arm C was halted at the sponsor's discretion (and not due to any safety issues) after enrollment of 19 subjects (3 in the 8 mg/kg MEDI-551 cohort and 16 who received 12 mg/kg MEDI-551). Of the 19 subjects there were only 7 responders, and there was about a 13% probability of meeting the protocol-specified target response rate of 50%.

Arm D

A sample size of approximately 26 subjects was planned for Arm D. Given an expected response rate of 50% for this cohort, this would provide 80% power at a significance level of 0.20 (2-sided) to exclude the historical response rate of 30% ([Zinzani et al, 2013](#); [Witzig et al, 2011](#)), and associated 80% confidence intervals for the response rate would have a precision of $\pm 13\%$.

Further enrollment was halted at the sponsor's discretion (and not due to any safety issues) after enrollment of 16 subjects. Of the 16 subjects there were only 3 responders, and there was about a 1% probability of meeting the protocol-specified target response rate of 50%.

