A total of 7 subjects were enrolled in Arm B dose-escalation, including 1 at a dose of 24 mg/kg. The dose escalation continued in Arm C as planned (8 mg/kg and 12 mg/kg) based on emerging PK and pharmacodynamic data that suggested a dose of 12 mg/kg, administered weekly during Cycle 1 and then monthly in subsequent cycles, was determined to be sufficient to saturate the B-cell sink and achieve full exposure. At the sponsor's discretion and not due to any safety issues, no further dose-escalation was conducted. The MTD was not reached and dose expansion was not conducted in Arm B.

Dose expansion: A sample size of 26 subjects was planned for each dose-expansion cohort in Arms B and C. Given an expected response rate of 50% for both cohorts, this would provide 80% power at a significance level of 0.20 (2-sided) to exclude the historical response rate of 30%, and associated 80% confidence intervals for the response rate would have a precision of $\pm 13\%$. The 30% historical response rate was selected for both Arms B and C expansion cohorts based on the following reported data:

- In relapsed CLL patients, objective response rates between 15% and 30% were reported for rituximab monotherapy (O'Brien et al, 2001; Mavromatis and Cheson, 2003).
- In DLBCL patients with 2 prior lines of therapy, response rates were only about 30% with single-agent rituximab (Coiffier et al, 1998; Wang et al, 2013; Churpek et al, 2013).

A total of 19 subjects were enrolled in Arm C. Of these 19 subjects there were only 7 responders, and there was about a 13% probability of meeting the protocol-specified target response rate of 50%; further enrollment to Arm C was therefore halted at the sponsor's discretion. The MTD was not reached and enrollment in Arm C was discontinued prior to dose expansion at the sponsor's discretion and not due to any safety issues.

Arm D

A sample size of approximately 26 subjects was planned for Arm D. Given an expected response rate of 50% for this cohort, this would provide 80% power at a significance level of 0.20 (2-sided) to exclude the historical response rate of 30% (Zinzani et al, 2013; Witzig et al, 2011), and associated 80% confidence intervals for the response rate would have a precision of $\pm 13\%$.

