- **Progression-free survival:** Progression-free survival will be measured from start of MEDI-551 administration until the first documentation of PD/relapse or death, whichever occurs first. Progression-free survival will be censored on the date of last disease assessment for subjects who have no documented PD/relapse or death prior to data cutoff, dropout, or the initiation of alternative anticancer therapy.
- **Overall survival:** Overall survival will be determined as the time from the start of MEDI-551 administration until death. For subjects who are alive at the end of study or lost to follow-up, OS will be censored on the last date when subjects are known to be alive.

The analysis methods will differ by the types of endpoints. For categorical endpoints, proportions will be summarized, 80% and 95% confidence intervals will be calculated using the Clopper-Pearson exact method. For time-to-event endpoints, Kaplan-Meier method will be used to describe the endpoints graphically and to estimate the median or the event rates at time of interest.

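### The 80% power and ±13% precision stated for 26 subjects in Arms B, C and D are normal-approximation figures; the Clopper-Pearson interval the protocol specifies gives 72% power and ±14%

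*Protocol*

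**What the plan says.** Protocol Section 7.5 plans the same size for three cohorts: "A sample size of 26 subjects was planned for each dose-expansion cohort in Arms B and C", and "A sample size of approximately 26 subjects was planned for Arm D". The alternative is a 50% response rate in each ("Given an expected response rate of 50% for both cohorts"; "Given an expected response rate of 50% for this cohort"). The claim attached to that size is that "this would provide 80% power at a significance level of 0.20 (2-sided) to exclude the historical response rate of 30" per cent, and that the "associated 80% confidence intervals for the response rate would have a precision of" ±13%. The Study Abstract repeats both figures for Arms B, C and D. No formula or test is named for these arms.

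The analysis is fixed in Section 7.4.3, where for categorical endpoints "80% and 95% confidence intervals will be calculated using the Clopper-Pearson exact method". For Arm A, by contrast, Section 7.5 does name its planning method: "The sample size estimation was based on the CR rate and the exact binomial test".

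**The concern.** Section 7.5 expresses the aim as excluding 30% and links it to the associated 80% confidence interval. Section 7.4.3 says how that interval will be computed. The quoted power and precision should therefore be properties of the 80% Clopper-Pearson interval with 26 subjects, and they are not.

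Response is part of a primary endpoint in Arms B, C and D. If the power is overstated, a negative result looks more informative than it is. With 26 subjects, one responder decides the matter: moving the cut-off from 12 to 11 takes power from 72.1% to 83.7% and upper-tail error from 6.0% to 12.5%. A reader working from the normal approximation would call 11/26 a success, while the reported exact interval would still contain 30%.

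**Working it through.** **Inputs (Protocol Sections 7.5 and 7.4.3).** n = 26; p0 = 0.30; p1 = 0.50; two-sided level 0.20, so 0.10 in the upper tail and z(0.90) = 1.2816; interval 80% Clopper-Pearson.

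**1. Reproducing the stated figures.**

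- Power, one-sample normal approximation: Φ{[(p1 − p0)√n − z√(p0(1 − p0))] / √(p1(1 − p1))} = Φ{[0.20 × 5.099 − 1.2816 × 0.4583] / 0.5} = Φ(0.865) = 80.6%.
- Sample size from the same formula with z(0.80) = 0.8416: [(1.2816 × 0.4583 + 0.8416 × 0.5) / 0.20]² = 25.4, rounded up to 26.
- Wald half-width at 50%: 1.2816 × √(0.25/26) = 12.6 points, which rounds to 13.

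Both figures and the sample size reproduce. That the sponsor used this approximation is inferred from the match.

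**2. The same quantities under the specified interval.** The 80% Clopper-Pearson lower limit for x responders is the 10th percentile of Beta(x, n − x + 1), and the upper limit is the 90th percentile of Beta(x + 1, n − x). The lower limit exceeds 30% when P(X ≥ x | 26, 0.30) is below 0.10.

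| Responders of 26 | 80% Clopper-Pearson interval | Excludes 30%? | P(X ≥ x) at 30% | P(X ≥ x) at 50% |
|---|---|---|---|---|
| 11 | 28.9% to 56.7% | no | 12.5% | 83.7% |
| 12 | 32.4% to 60.4% | yes | 6.0% | 72.1% |
| 13 | 35.9% to 64.1% | yes | 2.6% | 57.7% |

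The cut-off is 12/26. Power is 72.1%, the false-negative risk is 100 − 72.1 = 27.9%, and the upper-tail error is 6.0%. The half-width at 13/26 is (64.1 − 35.9)/2 = 14.1 points.

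**3. Is the shortfall only Clopper-Pearson conservatism?** No. The Wald interval, the one that yields ±13%, has a lower limit at 11/26 of 0.4231 − 1.2816 × √(0.4231 × 0.5769/26) = 29.9%. It also fails to exclude 30%, so it also needs 12/26 and also gives 72.1% power. The two stated figures do not describe one decision rule.

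**4. Sensitivity to size.** Exact power moves in steps. With 25 subjects the cut-off is 11, the error 9.8% and the power 78.8%. With 26 the cut-off rises to 12 and power drops. It first reaches 80% at n = 30 (cut-off 13, 81.9%), falls to 76.3% at 31 and is 81.2% at 32.

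**5. Arm A for comparison.** With n = 20, 5% against 20% and one-sided 0.10, the exact test needs at least 3 responders, with error 7.5% and power 79.4%. That agrees with the protocol's approximate 80%, so exact planning was used correctly elsewhere in the same section.

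**The case against.** The strongest reply has four parts.

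- **The arithmetic is sound.** Both figures follow from a standard formula, and planning by approximation while reporting exact intervals is common in small cohorts. This is right: the defect is a mismatch between planning method and specified analysis, not a slip of calculation.
- **72% is one reading.** Section 7.5 names no test, and Section 7.4.3 gives Clopper-Pearson as a summary method. A two-sided exact test ordered by likelihood rejects at 4 or fewer or 11 or more responders (total level 0.073 + 0.125 = 0.199 before rounding of the parts, power about 84%). A Wilson 80% interval at 11/26 has a lower limit of 30.7%. Both would support the stated power. Neither is named in the protocol, however, and each would contradict the reported Clopper-Pearson interval at 11/26. Section 7.5 itself ties exclusion of 30% to the associated interval.
- **The precision gap is small.** It is 14.1 − 12.6 = 1.5 points. Agreed; alone it would hardly merit comment.
- **Nothing now turns on it.** Enrollment closed on 30 September 2015, Arm B expansion was never run, and Arms C and D stopped at 19 and 16 subjects. At the reported responses the 80% Clopper-Pearson lower limits are 21.8% (7/19) and 7.1% (3/16), and Wilson gives 24.2% and 9.4%, so both methods leave 30% inside. The stopping reasons cite the 50% target. This stands and limits the practical weight, but Version 13.0 still presents the power claim next to its updated enrollment figures.

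**Conclusion.** The point holds. With 26 subjects, the analysis the protocol specifies gives 72.1% power rather than 80%, a 27.9% rather than 20% chance of missing a true 50% response rate, 6.0% upper-tail error rather than 10%, and ±14.1 rather than ±13 points. The power gap of about 8 points is the substance.

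This rests on reading exclusion of 30% through the equal-tailed 80% Clopper-Pearson interval, on 26 subjects evaluable for efficacy, and on a true rate of exactly 50%. It does not rest on how the sponsor arrived at 80%.

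For context only: with 16 subjects (Arm D, and Arm C at 12 mg/kg) the same rule needs at least 8 responders, with 59.8% power and a half-width of 18.2 points at 8/16. The conclusion does not depend on these figures.

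**What to change.** Amend the sample-size text for Arms B, C and D in Section 7.5 and in the Study Abstract along these lines: with 26 evaluable subjects, the 80% Clopper-Pearson interval excludes 30% if at least 12 respond; power is about 72% at a true rate of 50%, one-sided error about 6%, and precision about ±14 points at an observed rate of 50%.

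Alternatively, keep the 80% claim but name the less conservative test or interval that is to serve as the decision rule, quote its exact error and power, and say how it relates to the Clopper-Pearson interval being reported.

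The figures for 16 subjects may be added as context but are not essential; the exact intervals already planned show the precision achieved.

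The cost is wording in two places and a less favourable stated power. No additional subjects, procedures or changes to the planned intervals are needed.

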8 DIRECT ACCESS TO SOURCE DATA AND DOCUMENTS

The study will be monitored by MedImmune or its designee on a regular basis throughout the study period. During monitoring visits, the investigator will provide direct access to all source documentation relevant to the subject's participation in the study. Source documentation includes, but is not limited to, the subject's clinic and/or office chart, hospital chart, informed consent forms, treatment notes, laboratory reports, pharmacy records, radiographs, and any other records maintained to conduct and evaluate the clinical study. The investigator must also ensure that direct access to study documents be made available for study-related audits, IRB/IEC review, or regulatory inspection.

9 QUALITY CONTROL AND QUALITY ASSURANCE

9.1 Data Collection

As part of the responsibilities assumed by participating in the study, the investigator agrees to maintain adequate and accurate case histories for the subjects treated under this protocol. Case histories include CRFs and supporting data including, but not limited to, signed and dated informed consent forms, progress notes, hospital charts, nurse's notes, diary cards, laboratory reports, ECG strips, etc.

9.2 Study Monitoring

The primary source document for this study will be the subject's medical record. If separate research records are maintained by the investigator(s), both the medical record and the research records will be monitored/audited for the purposes of the study.

The investigator and institutions involved in the study will permit study-related monitoring and provide direct access to all study records and facilities. Adequate time and space for monitoring visits should be made by the investigator or other investigator site staff.

The monitor will visit study facilities at periodic intervals, in addition to maintaining necessary contact through telephone, e-mail, and letter. The monitor will assess subject enrollment and informed consent procedures; investigational product storage, dispensing, administration and accountability; compliance with protocol procedures; completeness and accuracy of data entered onto validated data collection instruments (paper CRF or electronic data screen) against original source documents; and the occurrence of AEs/SAEs. All aspects of the study will be carefully monitored for compliance with the protocol, applicable government regulations, GCP, and the site's standard operating procedures.

The monitor will discuss the conduct and progress of the study with the investigator and other site staff. The investigator must cooperate with the monitor to ensure that any problems noted in the course of the monitoring are resolved.

9.3 Audit and Inspection of the Study

During the conduct of the study, the sponsor or its representative may conduct audits of any data and facility participating in the study. The investigator and institutions involved in the study will permit such study-related audits and provide direct access to all study records and facilities. The investigator must maintain a comprehensive and centralized filing system of all study-related documentation that is suitable for inspection by the sponsor or its designated monitors, Quality Assurance monitors, or regulatory agency representatives. The investigator agrees to participate in audits conducted at a convenient time in a reasonable manner.

Government regulatory authorities may also perform inspections either during or after the study. In the event of an inspection by any regulatory authority, the investigator should promptly notify the sponsor. The investigator agrees to cooperate fully with inspections conducted by regulatory authorities and to allow representatives of the regulatory authority access to all study records. The investigator will forward to the sponsor a copy of any inspection records received.

10 ETHICS

10.1 Regulatory Considerations

The study will be conducted in accordance with the ICH guidelines on GCP, the GCPs applicable to any region where the study is conducted, and the ethical principles set forth in the Declaration of Helsinki. Good Clinical Practice is defined as a standard for the design, conduct, performance, monitoring, auditing, recording, analysis, and reporting of clinical studies in a way that provides assurance that the data and reported results are credible and accurate, and that the rights, safety, and well-being of study subjects are protected.

Per GCP, the protocol will be reviewed and approved by the IRB or IEC of each participating center prior to study initiation. Serious adverse events regardless of causality will be reported to the sponsor and to the IRB/IEC, and the investigator will keep the IRB/IEC informed as to the progress of the study.

The investigator will explain the nature of the study and will inform the subject/legal representative that participation is voluntary and that the subject can withdraw or be withdrawn from the study at any time. Written informed consent will be obtained from each subject/legal representative prior to the screening procedures to determine if study eligibility criteria are met. A copy of the signed consent form will be given to every subject/legal representative, and the original will be maintained with the subject's records.

10.2 Institutional Review Board or Independent Ethics Committee

A list of IRB/IEC members or a Statement of GCP Compliance should be obtained by the investigator and provided to the sponsor.

Any documents that the IRB/IEC may need to fulfill its responsibilities, such as protocol amendments, and information concerning subject recruitment, payment, or compensation procedures, or information from the sponsor will be submitted to the IRB/IEC. The IRB/IEC's written unconditional approval of the study protocol, the informed consent form(s), and any other written materials to be provided to subjects will be in the possession of the investigator and the sponsor before the study is initiated. The IRB/IEC's unconditional approval statement will be transmitted by the investigator to the sponsor prior to shipment of investigational product supplies to the site. This approval must refer to the study by exact protocol title and number, and should identify the documents reviewed and the date of review.

Protocol modifications or changes may not be initiated without prior written IRB/IEC approval except when necessary to eliminate immediate hazards to the subjects or when the

change(s) involves only logistical or administrative aspects of the study. Such modifications will be submitted to the IRB/IEC and written verification that the modification was submitted should be obtained.

The IRB/IEC must be informed by the investigator of informed consent form changes or revisions of other documents originally submitted for review; serious and/or unexpected adverse experiences occurring during the study; new information that may affect adversely the safety of the subjects or the conduct of the study; an annual update and/or request for re-approval; and when the study has been completed.

10.3 Informed Consent

Freely given informed consent will be obtained and documented for all subjects under this protocol (or a subject's legally authorized representative, if the subject is unable to provide informed consent) in accordance with the ICH guidelines on GCP, the GCPs applicable to any region where the study is conducted, and the ethical principles set forth in the Declaration of Helsinki.

Information should be given in both oral and written form, and subjects or their legal representatives must be given ample opportunity to inquire about details of the study. Subjects or their legal representatives must be informed of the following:

- The study involves research.
- The aims, expected benefits, possible risks (including a statement that the particular treatment or procedure may involve risks to the subject or the fetus of the subject, if the subject should become pregnant) that are currently unforeseeable.
- The study procedures to be followed and alternative treatment available to them. Subjects or their legal representatives must receive an explanation as to whether any compensation and any medical treatments are available if injury occurs and, if so, what they consist of, or where further information may be obtained.
- Who to contact for answers to any questions relating to the research project.
- Participation is voluntary and that they are free to withdraw or withdraw their child from the study for any reason at any time, without penalty or loss of benefits to which they are otherwise entitled.
- The extent of the confidentiality of subject records must be defined, and subjects or their legal representatives must be informed that applicable data protection legislation will be complied with.
- The monitor(s), auditor(s), IRB/IEC members, and the regulatory authorities will be granted direct access to the subject's original medical records for verification of clinical study procedures and/or data, without violating the confidentiality of the subject, to the

extent permitted by the applicable laws and regulations and that, by signing a written informed consent form, the subject or the subject's legally acceptable representative is authorizing such access.

The consent form generated by the investigator must be approved by the IRB/IEC and be acceptable to MedImmune. Consent forms must be written so as to be understood by the prospective subject/legal representative. Informed consent will be documented by the use of a written consent form approved by the IRB/IEC and signed and dated by the subject or the subject's legally authorized representative, and by the person who conducted the informed consent discussion. The signature confirms the consent is based on information that has been understood. Each subject's signed informed consent form must be kept on file by the investigator for possible inspection by regulatory authorities and/or MedImmune professional and regulatory compliance persons. The subject or the subject's legally acceptable representative should receive a copy of the signed and dated written informed consent form and any other written information provided to the subject, and should receive copies of any signed and dated consent form updates and any amendments to the written information provided to subjects.

